7.3 Visit Schedule And Assessments

Screening assessments and procedures to be performed on study scheduled visits are outlined in Section 2 Table of Study Assessments. All screening assessments should be completed within 28 days from consent and prior to Cycle 1 Day 1. The day 14 visit can occur \pm 3 days.

An unscheduled visit can occur at any time during the study. For all unscheduled visits, source documents must be maintained and the date for the visit and any data generated must be recorded on the appropriate CRF.

Investigators may also assess participants via telemedicine at any point the investigator, local health or government authorities and/or other Hopkins authorities deem it appropriate. In these cases, an assessment may not include a physical exam or samples collection. All efforts should be made to perform in person visits if possible.

7.4 Follow-Up

Subjects who discontinue study treatment for any reason will undergo a safety assessment approximately 30 days post the last dose of study drug.

7.5 Serious Adverse Event (SAE)Definition

A serious adverse event (SAE) is one that at any dose (including overdose):

- Results in death
- Is life-threatening¹
- Requires inpatient hospitalization or prolongation of existing hospitalization
- Results in persistent or significant disability or incapacity²
- Is a congenital anomaly or birth defect
- Is an important medical event³
- Pregnancy

¹“Life-threatening” means that the subject was at immediate risk of death at the time of the serious adverse event; it does not refer to a serious adverse event that hypothetically might have caused death if it were more severe.

²“Persistent or significant disability or incapacity” means that there is a substantial disruption of a person’s ability to carry out normal life functions.

³Medical and scientific judgment should be exercised in deciding whether expedited reporting is appropriate in situations where none of the outcomes listed above occurred. Important medical events that may not be immediately life-threatening or result in death or hospitalization but may jeopardize the patient or may require intervention to prevent one of the other outcomes listed in the definition above should also usually be considered serious. Examples of such events include allergic bronchospasm requiring intensive treatment in an emergency room or at home, blood dyscrasias or convulsions that do not result in inpatient hospitalization, or the development of drug dependency or drug abuse. A new diagnosis of cancer during the course of a treatment should be considered as medically important.

7.6 Adverse Drug Reaction Reporting

Toxicity will be scored using CTC Version 4.0 for toxicity and adverse event reporting. A

copy of the CTC Version 4.0 can be downloaded from the CTEP homepage (<http://ctep.info.nih.gov>). All appropriate treatment areas have access to a copy of the CTC Version 4.0. All adverse events (AEs), whether observed by the investigator or

reported by the patient, must be recorded with details about the duration and intensity of each episode, the action taken with respect to the test drug, and the patient's outcome. The investigator must evaluate each adverse experience for its relationship to the test drug and for its seriousness.

The principal investigator is responsible for evaluating all adverse events, obtaining supporting documents, and determining that documentation of the event is adequate. The principal investigator is responsible for determining the severity and relationship of the adverse event to the investigational drug. The principal investigator may delegate these duties to sub-investigators and must assure that these sub-investigators are qualified to perform these duties under the supervision of the principal investigator.

All adverse events will be recorded in the subject's Case Report Form and in the study data base. The detailed description of the event will include appropriately graded severity of the adverse event and its relationship to the study drug.

Severity of adverse events will be categorized by toxicity grade according to the NCI Common Terminology Criteria for Adverse Events version 5.0 available at <http://ctep.cancer.gov/reporting/ctc.html>

7.6.1 Adverse events not listed in the NCI Common Terminology Criteria

Adverse events not listed in the NCI Common Terminology Criteria for Adverse Events will be evaluated using the following criteria:

Grade 1, Mild: Awareness of symptom, but easily tolerated; usually transient requiring no special treatment; does not interfere with usual status or activities

Grade 2, Moderate: May be ameliorated by simple therapeutic measures; may interfere with usual activities

Grade 3, Severe: Incapacitating, inability to perform usual activities

Grade 4, Life-threatening/Disabling: Subject was at risk of death or significant disability at the time of the event

Grade 5, Death related to AE

7.6.2 Relationship of the Adverse Event to the Investigational Drug

Relationship of the adverse event to the investigational drug will be determined by the principal investigator, and will be categorized as:

Not Related: The adverse event is clearly related to other factors such as the subject's clinical state, environmental factors, or other modes of therapy or concomitant drugs administered to the subject.

Possible: The adverse event follows a reasonable temporal sequence from administration of the study drug, and/or follows a known response pattern to the study drug, but could readily have been produced by the subject's clinical state, environmental factors, or other modes of therapy or concomitant drugs administered to the subject.

Probable: The adverse event follows a reasonable temporal sequence from administration of the study drug and follows a known response pattern to the study drug, and cannot readily have been produced by the subject's clinical state, environmental factors, or other modes of therapy or concomitant drugs administered to the subject.

The investigator must appraise all abnormal clinical laboratory results for their clinical significance. In accordance with FDA requirements and guidelines, we shall report the most frequent and most serious adverse events (SAEs) suffered by subjects on the clinical trial.

If any abnormal laboratory result is considered clinically significant and possibly drug related, the investigator must provide details about the action taken with respect to the study drug and about the patient's outcome.

7.7 Expedited Reporting By Investigator To Celgene

For the purpose of regulatory reporting, Celgene Drug Safety will determine the expectedness of events of being related to lenalidomide based on the Investigator Brochure. In the United States, all suspected unexpected serious adverse reactions (SUSARs) will be reported in an expedited manner in accordance with 21 CFR 312.32.

Serious adverse events (SAE) are defined above. The investigator must inform Celgene in writing using a Celgene SAE form or MEDWATCH 3500A form of any SAE within 24 hours of being aware of the event. The written report must be completed and supplied to Celgene by facsimile within 24 hours. The initial report must be as complete as possible, including an assessment of the causal relationship between the event and the investigational product(s). Information not available at the time of the initial report (e.g., an end date for the adverse event or laboratory values received after the report) must be documented on a follow-up report. A final report to document resolution of the SAE is required. The Celgene tracking number (**RV-CL-MM-PI-005749**) and the institutional protocol number should be included on SAE reports (or on the fax cover letter) sent to Celgene. A copy of the fax transmission confirmation of the SAE report to Celgene should be attached to the SAE form, and retained with the patient records.

7.8 Pregnancies

Pregnancies and suspected pregnancies (including a positive pregnancy test regardless of age or disease state) of a female subject occurring while the subject is on IP, or within 28 days of the subject's last dose of IP, are considered immediately reportable events. IP

is to be discontinued immediately. The pregnancy, suspected pregnancy, or positive pregnancy test must be reported to Celgene Drug Safety immediately by facsimile, or other appropriate method, using the Pregnancy Initial Report Form, or approved equivalent form. The female subject may be referred to an obstetrician-gynecologist (not necessarily one with reproductive toxicity experience) or another appropriate healthcare professional for further evaluation.

The Investigator will follow the female subject until completion of the pregnancy, and must notify Celgene Drug Safety immediately about the outcome of the pregnancy (either normal or abnormal outcome) using the Pregnancy Follow-up Report Form, or approved equivalent form.

IF THE OUTCOME OF THE PREGNANCY WAS ABNORMAL (E.G., SPONTANEOUS OR THERAPEUTIC ABORTION), THE INVESTIGATOR SHOULD REPORT THE ABNORMAL OUTCOME AS AN AE. IF THE ABNORMAL OUTCOME MEETS ANY OF THE SERIOUS CRITERIA, IT MUST BE REPORTED AS AN SAE TO CELGENE DRUG SAFETY IMMEDIATELY BY FACSIMILE, OR OTHER APPROPRIATE METHOD, WITHIN 24 HOURS OF THE INVESTIGATOR'S KNOWLEDGE OF THE EVENT USING THE SAE REPORT FORM, OR APPROVED EQUIVALENT FORM.

All neonatal deaths that occur within 28 days of birth should be reported, without regard to causality, as SAEs. In addition, any infant death after 28 days that the Investigator suspects is related to the in utero exposure to the IP should also be reported to Celgene Drug Safety immediately by facsimile, or other appropriate method, within 24 hours of the Investigator's knowledge of the event using the SAE Report Form, or approved equivalent form.

Male Subjects

If a female partner of a male subject taking investigational product becomes pregnant, the male subject taking lenalidomide should notify the Investigator, and the pregnant female partner should be advised to call their healthcare provider immediately.

7.9 Celgene Drug Safety Contact Information:

Celgene Corporation
Global Drug Safety and Risk Management
[name]
[name]
[name]
[contact]
E-mail: [contact]

7.10 Investigator Reporting Responsibilities

The conduct of the study will comply with all FDA safety reporting requirements. If the FDA has granted an IND number, it is a requirement of 21 CFR 312.33, that an annual report is provided to the FDA within 60-days of the IND anniversary date. 21 CRF 312.33

provides the data elements that are to be submitted in the report. The Annual Report should be filed in the study's Regulatory Binder, and a copy provided to Celgene Corporation as a supporter of this study as follows:

Celgene Corporation
Attn: Medical Affairs Operations
[name]
[name]
[name]
[contact]

All adverse experience reports must include the patient number, age, sex, weight, severity of reaction (e.g. mild, moderate, severe), relationship to drug (e.g. probably related, unknown relationship, definitely not related), date and time of administration of test medications and all concomitant medications, and medical treatment provided. The investigator is responsible for evaluating all adverse events to determine whether criteria for "serious" and as defined above are present. The investigator is responsible for reporting adverse events to Celgene as described below.

7.11 Report Of Adverse Events To The Institutional Review Board

The Principal Investigator is required to notify the Institutional Review Board (IRB) by facsimile using the serious adverse experiences CRF within 7 calendar days of observing or learning of a serious and unexpected adverse event. A mailed hard copy to the IRB (with a copy to the study monitor) must be submitted within 15 calendar days of observing or learning of the event. The written report should identify all safety reports previously filed with the IND concerning a similar adverse reaction and should analyze the significance of the adverse reaction in light of the previous, similar reports.

7.12 Investigator Reporting To The FDA

Adverse drug reactions that are **Serious, Unlisted/unexpected, and at least possibly associated to the drug**, and that have not previously been reported in the Investigators Brochure, or reference safety information documents should be reported promptly to the Food and Drug Administration (FDA) in writing by the Primary Investigator (PI) engaged in clinical research. A clear description of the suspected reaction should be provided along with an assessment as to whether the event is drug or disease related.

The PI must notify the FDA by telephone or fax of any unexpected, fatal or life threatening experience associated with the use of the drug as soon as possible but no later than 7 days of the sponsors initial receipt of the information.

7.13 Adverse Event Updates/Ind Safety Reports

Celgene shall notify the Primary Investigator via an IND Safety Report of the following information:

- Any AE associated with the use of study drug in this study or in other studies that is both serious and unexpected.
- Any finding from tests in laboratory animals that suggests a significant risk for human subjects including reports of mutagenicity, teratogenicity, or carcinogenicity.

The Primary Investigator shall notify his/her IRB/EC promptly of these new serious and unexpected AE(s) or significant risks to subjects.

The Primary Investigator must keep copies of all AE information, including correspondence with Celgene and the IRB/EC, on file.

8 RESPONSE CRITERIA

Baseline tumor assessments must occur within \leq 28 days of initiation of the study as indicated in Section 2, Schedule of Study Assessments.

Measurements of anti-myeloma efficacy will occur prior to the initiation of each cycle of lenalidomide. Myeloma response assessments will be based on the International Uniform Criteria.⁵²

Patients with confirmed progressive disease will be eligible to cross over on to the vaccine arm based on clinical judgement, available response data, and the PI's discretion, or be removed from study treatment.

Research blood and marrow will be used to assess responses during the trial. This will likely include but are not limited to:

1. Tumor specific immunity
2. Assessment of myeloid derived suppressor cell (MDSC) numbers and function by flow cytometry and T cell proliferation assays.
3. Activation markers on T cells by flow cytometry
4. Clonogenic myeloma precursors by flow cytometry.
5. Minimal Residual Disease (MRD) testing

The major purpose of this study is to determine whether the addition of an allogeneic myeloma vaccine can augment clinical responses to Lenalidomide.

9 PROTOCOL AMENDMENTS/DEVIATIONS

9.1 Protocol amendments

Any amendment to this protocol must be agreed to by the Principal Investigator and reviewed by Celgene. Amendments should only be submitted to IRB/EC after consideration of Celgene review. Written verification of IRB/EC approval will be obtained before any amendment is implemented.

9.2 Protocol deviations

When an emergency occurs that requires a deviation from the protocol for a subject, a deviation will be reported only for that subject. A decision will be made as soon as possible to determine whether or not the subject (for whom the deviation from protocol was effected) is to continue in the study treatment. The subject's medical records will completely describe the deviation from the protocol and state the reasons for such deviation. In addition, the Investigator will notify the IRB/EC in writing of such deviation from protocol.

Non-emergency minor deviations from the protocol will be permitted with approval of the Principal Investigator.

10 DATA MANAGEMENT

10.1 Analyses and Reporting

Patients will be considered evaluable for safety and efficacy once they have initiated any study treatment (lenalidomide, vaccine and/or Prevnar vaccine).

Safety will be monitored continuously throughout the trial. Efficacy will be analyzed upon trial completion. No interim efficacy analyses are planned.

10.2 Study monitoring and Auditing

The protocol will be monitored internally by the Principal Investigator and externally via the SKCCC Compliance Monitoring Program which provides external monitoring for JHU-affiliated sites in accordance with SKCCC DSMP (Version 6.0, 02/21/2019). The Institution's Safety Monitoring Committee (SMC) Subcommittee will determine the level of patient safety risk and level/frequency of monitoring.

10.2.1 Investigator Responsibilities

The Primary Investigator's responsibilities are set out in the ICH guideline for Good Clinical Practice (GCP) and in the US Code of Federal Regulations.

Study data will be entered onto a dedicated GVAX database. The Primary Investigator will permit study-related monitoring visits and audits by Celgene or its representatives, IRB/IEC review, and regulatory inspection(s) (e.g., FDA, EMEA, TPP), providing direct access to the facilities where the study took place, to source documents, to CRFs, and to all other study documents.

The Primary Investigator, or a designated member of the Investigator's staff, must be available during monitoring visits to review data, to resolve any queries and to allow direct

access to the subject's records (e.g., medical records, office charts, hospital charts, and study related charts) for source data verification. The data collection must be completed prior to each monitoring visit and be made available to the Celgene representative so that the accuracy and completeness may be checked.

10.2.2 Data Safety Monitoring Board (DSMB)

The role of the DSMB will be to monitor the study for safety and toxicity issues regarding the combination of Lenalidomide with a cellular myeloma vaccine. Interim analysis of toxicity, outcome, and ongoing scientific investigations will be performed at least annually by the Sidney Kimmel Comprehensive Cancer Center Data Safety Monitoring Board (SKCCC DSMB). The SKCCC DSMB Recommendation letter will state the timeline for the next required review. The SKCCC DSMB will review aspects of this trial that are outlined in the responsibilities section of the Data and Safety Monitoring Board (DSMB) Guidance. If the committee decides that amendments should be made to this trial, recommendations will be made in writing to the study Principal Investigator. The study team will submit modifications to the IRB within 60 days of receipt from the DSMB. The Associate Director of Clinical Research will arbitrate any disagreements between the DSMB and the study Principal Investigator. These changes may include early termination of accrual if deemed appropriate.

11 BIOSTATISTICAL ANALYSIS

11.1 Sample Size Considerations

The primary endpoint of this phase II study is progression free survival (PFS). The primary analysis will compare the control arm (lenalidomide plus placebo) versus the pooled allogenic myeloma vaccine arms (with and without Prevnar). In a prior study, the median PFS for patients on Len containing therapy was 17.9 months. Patients will be accrued over the course of 2 years with a minimum follow-up of 3 years (i.e. all patients will have 3-5 years of follow-up). A sample size of 54 patients (18 placebo vs 36 allogenic myeloma) would provide 80% power to detect an increase in the median PFS from 18 months in the control arm to 42.8 months in the pooled vaccine arm ($HR = 0.4199$) based upon a log-rank test assuming a two-sided type I error rate of 10% and a loss to follow-up rate of 1% per year (5% overall). The accrual rate is expected to be 2.3 per month. Due to the small sample size, no interim efficacy analysis is planned at this time.

Our principal secondary endpoints will be conversion from “near CR” (M-spike at or below 0 but IFE positive), to “true CR” (IFE negative), and conversion from MRD positive status to MRD negative status. The trial will accrue patients for a total $n=18$ per arm at single center for a period two years, while trial duration for every patient enrolled will be 3 years. The analysis will be performed on the intention to treat population.

11.2 Statistical Analyses

The efficacy and safety analysis populations will include all patients that received at least one dose of their assigned treatment. The primary analyses will compare the control arm with the pooled vaccine arm. Secondary analyses will compare the two vaccine arms to one another and to the control arm.

Demographic and disease characteristics will be summarized overall and within each treatment group using medians and ranges for continuous variables and counts and proportions for categorical variables.

The primary outcome (PFS) is defined as the time from randomization until progression or death. Individuals who do not have an event will be censored at the date of last assessment. Kaplan-Meier estimates of the survival function will be used to compare the two treatment groups graphically as well as to provide estimates of the median PFS and the proportion who have progressed at key time points (e.g. 1-, 2-, and 3-years) with 90% confidence intervals. Log-rank tests will be used to compare the treatment groups and Cox proportional hazards models will be used to examine the effects of specific risk factors of interest and their interaction with treatment (e.g. vaccine by MRD status interactions). If the proportional hazards assumption is violated, the piecewise proportional hazards models or other semi-nonparametric approaches will be used. Key secondary endpoints include conversion from “near CR” (M-spike at or below 0 but IFE positive), to “true CR” (IFE negative), and conversion from MRD positive status to MRD negative status. These and other time to event outcomes including will be analyzed in a similar manner to the primary outcome as well as with competing risk models to account for death or progression.

Tumor immunology assessments will be made at baseline and on day 14 of cycles 3, 6, and 12 (the 1-year assessment). At each time point, graphical (e.g. boxplots over time, spaghetti plots) and numeric (e.g. median, range, proportion) summaries will be used to explore the continuous (e.g. T cell populations) and binary (e.g. tumor specific immunity) outcomes. If appropriate, transformations (e.g. log) will be used to address skewness in the data. Cross-sectional comparisons will be made using t-tests, Kruskal-Wallis tests, or linear regression and Chi-squared tests, Fisher’s exact test, or logistic regression for continuous and categorical outcomes, respectively. Generalized estimating equations and mixed effects models will be used to formally model the behavior over time and compare treatment groups and/or risk factors while adjusting for repeated measurements within each individual. The association between baseline tumor measurement as well as changes in tumor measurements over time and clinical outcomes will be assessed using Cox proportional hazards models.

Toxicity will be scored using NCI CTC Version 4.0 for toxicity and adverse events. All toxicities will be summarized overall, by treatment group, and within subgroups of interest (e.g. true CR status, MM type). The number of toxicities and number of affected patients will be tabulated by type, grade, and relatedness to study treatment (overall and for each treatment). In addition to counts and proportions, the toxicity rates will be modeled and compared between treatment groups and subgroups of interest using Poisson regression or Negative Binomial regression, as appropriate.

11.3 Toxicity Stopping Guidelines:

The proportion of unacceptable toxicities will be continuously monitored in each arm separately. Unacceptable toxicities include hematologic toxicities of lenalidomide: low neutrophils (ANC <1000) and low platelets (<50K), for which we would hold the vaccine administration, as well as vaccine related toxicities which include: grade 3/4 local reactions (erythema, swelling, pain) and systemic symptoms (fevers, rash) (Refer to **7.6.1** and **7.6.2** for guidelines on attribution of toxicities).

Unacceptable toxicities as scored using **NCI CTCAE V5.0** include:

- Any laboratory or clinical organ dysfunction \geq Grade 3
- Abnormalities of coagulation (prolonged prothrombin, partial thromboplastin and clotting times \geq Grade 3)
- Autoimmune disease reactivation or development \geq Grade 2
- Immune system disorders including myalgias or headaches \geq Grade 3
- Immune system disorders including allergic or hypersensitivity reactions such as rash, or fever \geq Grade 3
- Immune system disorders including anaphylaxis or anaphylactoid reactions (eg. Wheezing, urticarial, hypotension) \geq Grade 3
- General disorders and administration site conditions including injection site reactions such as tenderness with or without associated symptoms (e.g., warmth, erythema, itching, and malaise) \geq Grade 3
- Any other undefined or unanticipated adverse event \geq Grade 3
- Any death on study

If the levels of unacceptable toxicities is too high (i.e. a high probability that they exceed the maximum threshold of 30%), then enrollment will be suspended pending review by the PI, DSMB, and Celgene. Any death on study within 30 days of GVAX administration will lead to suspension of enrollment pending review by the PI, DSMB, and Celgene.

A Bayesian stopping guideline will be used to assess the level of unacceptable toxicity. We expect the rate of unacceptable toxicities to be 25%. Hence a Beta(1, 3) prior was used. After the first three patients are recruited, toxicity will be monitored continuously. Accrual will be suspended if the probability that the unacceptable toxicity rate exceeds 30% is 0.70 or higher. Table 11.1 shows the number of toxicities needed to halt accrual.

Table 11.1. The number of toxicities needed to trigger stopping guidelines throughout the course of the study.

Number of Subjects Per Treatment Arm	Number of toxicities needed to trigger re-evaluation
3-4	3
5-7	4
8-10	5
11-13	6
14-16	7
17-18	8

The operating characteristics of these stopping guidelines were generated based upon 5000 simulations (Table 11.1).

Table 11.2. Probability of triggering stopping guidelines based upon range of underlying toxicity rates.

True Toxicity (DLT) Risk	Prob. Declare Treatment Too Toxic	Avg. Sample Size
0.05	<0.1%	18.0
0.10	0.4%	18.0
0.15	2.7%	17.7
0.20	7.6%	17.2
0.25	15.2%	16.5
0.30	27.7%	15.4
0.35	44.0%	13.8
0.40	59.5%	12.3
0.45	74.2%	10.7

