5 STUDY OBJECTIVES AND ENDPOINTS

5.1 Study objectives:

Primary:

- To compare the 2-year progression free survival of patients with multiple myeloma in a near complete remission (nCR) or complete remission (CR) who are also minimal residual disease positive (MRD+), treated with an allogeneic myeloma vaccine in combination with lenalidomide (with or without Prevnar vaccine) versus placebo in combination with lenalidomide.

Secondary:

- To compare the 2-year progression free survival for those treated with or without Prevnar in addition to an allogeneic myeloma vaccine and lenalidomide
- Determine rate of conversion of nCR to true CR
- Determine rate of conversion of MRD positivity to MRDnegativity
- Determine time to response
- Determine the progression free survival at 3 and 5years
- Evaluate toxicity of the allogeneic myeloma vaccine
- Measure tumor specific immunity and correlate with systemic immunity

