6 INVESTIGATIONAL PLAN

6.1 Overall design:

[figure not shown]
Patients with newly diagnosed or relapsed/refractory multiple myeloma (NDMM or RMM) in CR or nCR who meet appropriate criteria will be eligible for enrollment.

Specifically:

[figure not shown]
- Patients with NDMM who have completed 6 cycles of treatment with any lenalidomide containing regimen (e.g. KRD, VRD, Rd, BiRD or R alone) and who have been in CR or nCR for ≥ 3 months.
- Patients with MM who have undergone ASCT will only become eligible ≥ 12 months following date of cell infusion, will have been on lenalidomide maintenance for ≥ 6 cycles prior to enrollment, and continue to meet criteria for CR or nCR for ≥ 3 months.
- Patients with RMM will need to have completed at least 6 cycles of current therapy with a lenalidomide containing regimen, and be in CR or nCR for ≥ 3 months.
- All patients must be MRD positive at 10^{-4} by NGS sequencing at enrollment

Eligible patients who go on to enroll will be randomized in a 1:1:1 fashion to one of three arms. All patients will continue on a standard dose of lenalidomide (15mg daily, to be adjusted as clinically necessary), given on days 1 – 21 of a 28 day cycle. Patients on the myeloma vaccine arm will receive injections with an allogeneic myeloma vaccine administered intradermally on day 14 of cycles 1, 2, 3, 6 and annually for a minimum of 36 months in addition to lenalidomide unless otherwise clinically indicated, or until progression. Patients on myeloma plus Prevnar vaccine arm will receive injections of both allogenic myeloma vaccine, intradermally, and Prevnar vaccine, intramuscularly, on day 14 of cycles 1, 2, 3, 6, and annually for a minimum of 36 months in addition to lenalidomide unless otherwise clinically indicated, or until progression. Patients on the myeloma vaccine placebo arm will receive myeloma vaccine placebo on the same schedule as allogeneic myeloma vaccine. If assigned to either of the two arms that do not include Prevnar, then patients will receive placebo in lieu of Prevnar on the same schedule. The placebo will be saline. The study schema is shown below:

SCHEMA

Vaccination Schedule

Allogeneic Myeloma Vaccine or placebo administration – in months: 1, 2, 3, 6, 12, 24, and 36
 Prevnar or Prevnar placebo administration – concurrent with myeloma vaccine administration
 MRD testing – enrollment, 6 mo, 12 mo, annually for the duration of study

6789

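### Section 11.2 permits arm comparisons of continuous immune measures that leave out the baseline sample, and does not say how baseline enters the regression, GEE or mixed models

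*Combined protocol and SAP*

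**What the plan says.** Section 5.1 lists among the secondary objectives: "Measure tumor specific immunity and correlate with systemic immunity". Section 11.2 sets the timing: "Tumor immunology assessments will be made at baseline and on day 14 of cycles 3, 6, and 12", the last being the one-year visit.

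The same paragraph then gives two kinds of analysis.

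- **Visit by visit:** "Cross-sectional comparisons will be made using t-tests, Kruskal-Wallis tests, or linear regression" for continuous outcomes, with chi-squared, Fisher's exact or logistic regression for categorical ones. No covariate is named.
- **Over time:** "Generalized estimating equations and mixed effects models will be used to formally model the behavior over time and compare treatment groups and/or risk factors". These models are to allow for the correlation between a patient's visits. Baseline is one of the scheduled assessments, but its place in these models is not stated.

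Baseline is named as a predictor only for the Cox models, which address a different question: "The association between baseline tumor measurement as well as changes in tumor measurements over time and clinical outcomes". Those models relate measurements to clinical outcome and do not compare arms.

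The plan does not say which of these analyses is the main arm comparison. On size, section 6.1 has "Eligible patients who go on to enroll will be randomized in a 1:1:1 fashion to one of three arms", with 18 per arm. The only power statement, in section 11.1, is for PFS: "A sample size of 54 patients (18 placebo vs 36 allogenic myeloma) would provide 80% power".

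**The concern.** With 18 patients per arm, much of the spread in a post-vaccine immune measure may be spread that was already there before vaccination. A comparison that uses each patient's own baseline value removes that part; a t-test or Kruskal-Wallis test on the later value leaves it in the error term. The baseline sample is already being collected, so the lost precision would cost nothing to recover.

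The models that could recover it are left open. A longitudinal model can be set up so that it gains from baseline at any correlation, or so that it loses when the correlation is low. What is at stake is the width of the intervals on the vaccine's immune effect, and whether the analyst settles the method before or after seeing the data.

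**Working it through.** **1. The plan's own figure.** No power, SD, correlation or alpha is given for any immune measure. The one stated figure, 80% power for PFS, reproduces. With exponential PFS (medians 18 and 42.8 months), 24 months' uniform accrual, 36 months' minimum follow-up and 1% loss per year, the event probabilities are 0.825 (control) and 0.528 (vaccine). Then |ln 0.4199| / √(1/(18×0.825) + 1/(36×0.528)) = 0.868/0.346 = 2.51. Subtracting 1.645 gives 0.86, which is 80.5% power. Nothing below depends on it.

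**2. Single visit, continuous outcome.** Let r be the correlation between baseline and follow-up, with equal SDs.

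- Variance with baseline adjustment / variance without = 1 - r². The SE ratio is √(1 - r²).
- Difference detectable with 80% power, in SDs = (1.645 + 0.842) × √(1/n₁ + 1/n₂) × √(1 - r²).

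Assumptions, none from the documents: r of 0.3 to 0.7, two-sided alpha 10% (borrowed from PFS), and a true difference of 0.8 SD for the power column.

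| r | 1 - r² | SE ratio | SE smaller by | Detectable, 18 vs 18 | Detectable, 18 vs 36 | Power, 18 vs 18 |
|---|---|---|---|---|---|---|
| unadjusted | 1 | 1 | – | 0.829 | 0.718 | 77.5% |
| 0.3 | 0.91 | 0.954 | 5% | 0.791 | 0.685 | 80.8% |
| 0.5 | 0.75 | 0.866 | 13% | 0.718 | 0.622 | 87.0% |
| 0.7 | 0.51 | 0.714 | 29% | 0.592 | 0.513 | 95.7% |

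**3. How baseline enters the model.** Four estimators were simulated with 18 per arm, one baseline and one follow-up value, unit SDs and 4,000 runs. The table shows the SE of the arm difference. The common-baseline-mean model was fitted with the covariance treated as known.

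| r | Follow-up only | Change score | ANCOVA | Common baseline mean |
|---|---|---|---|---|
| 0.3 | 0.333 | 0.396 | 0.323 | 0.318 |
| 0.5 | 0.331 | 0.327 | 0.289 | 0.285 |
| 0.7 | 0.338 | 0.261 | 0.244 | 0.240 |

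The change-score column is what a longitudinal model yields, with complete data, when baseline means are free to differ by arm and the effect is the arm-by-time contrast. It is worse than follow-up alone at r = 0.3, about equal at 0.5 and better at 0.7. ANCOVA and the common-baseline-mean model are better at all three. Section 11.2 is compatible with any of the four columns.

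**4. The cost of the covariate.** The simulated ANCOVA figures include it: 0.323/0.333 = 0.97, 0.289/0.331 = 0.87 and 0.244/0.338 = 0.72. The reductions are therefore about 3%, 13% and 28%. Adding the two stratification factors as well, if they do not predict the outcome, takes the variance ratio at r = 0.3 from the nominal 0.91 to about 0.95 when they are balanced across arms and to about 1.0 when they are not. At r = 0 such adjustment raises the variance, with ratios of 1.03 to 1.10.

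**The case against.** The strongest reply is that the plan does not confine itself to unadjusted tests. The sentence that names them also allows linear regression, and its categorical counterpart allows logistic regression; either can carry a baseline term. The next sentence makes GEE and mixed models the formal comparison of arms, over visits that include baseline. A reader might infer from the t-tests and Kruskal-Wallis tests that the plan ignores baseline. The documents do not support that. A mixed model with a common baseline mean is within the plan as written and already recovers the gain. What stands is that the plan does not commit to it, and that another permitted specification does worse than no adjustment at low r.

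Three other stronger readings also fail.

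- **Bias.** At 18 vs 18 the baseline mean difference has SE √(2/18) = 0.333 SD, so a chance imbalance above 0.5 SD (1.5 standard errors) occurs about 13% of the time per measure. A reader might infer that unadjusted tests would report such imbalance as a vaccine effect too often. Under randomization they do not: the standard error already allows for it and type I error is kept.
- **A fixed loss of patients.** 54/(1 - r²) gives 59, 72 and 106 at r = 0.3, 0.5 and 0.7. A reader might take these as the sample size the plan forgoes. They apply only against an unadjusted single-visit test of a continuous outcome at assumed correlations, not against the planned longitudinal models.
- **Binary outcomes.** Section 11.2 gives tumor-specific immunity itself as an example of a binary outcome, and 1 - r² does not carry over. In logistic regression a prognostic baseline status raises the SE of the treatment coefficient (ratios of 1.03 to 1.31 in large-sample simulation), because the conditional effect is larger too.

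The low rank of these measures must also be granted. The section 5.1 objective is to measure and correlate, the key secondary endpoints in section 11 are CR and MRD conversion, and the immune summaries are exploratory.

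**Conclusion.** The point holds as a free gain in precision. As written, section 11.2 permits comparisons of continuous immune measures that either omit baseline or use it inefficiently, and it fixes neither the main method nor the role of baseline. Against an unadjusted single-visit test, adjustment would shrink the SE by about 5%, 13% or 29% at r of 0.3, 0.5 or 0.7, or about 3%, 13% and 28% after estimating the covariate. Against a mixed model with a common baseline mean there is nothing left to gain.

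These sizes rest on assumed correlations; the documents give neither a correlation nor an SD, and at low r the benefit is little or none. They cover continuous outcomes only. Validity is not in question, and the PFS conclusion is untouched.

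**What to change.** In section 11.2, for continuous immune outcomes:

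- Name one main arm comparison on the (log-)transformed scale: ANCOVA on the post-vaccine value with the same measure at baseline as covariate, or a mixed model over all visits with baseline either as a covariate or as a response with a common mean across arms.
- Say that the t-tests and Kruskal-Wallis tests are descriptive.
- Settle this before unblinding, so that the method is not chosen after the results are seen.

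The cost is wording and programming, plus a few degrees of freedom, with little or no return if the correlation proves low. No new sample or visit is needed. A patient with no baseline value drops out of ANCOVA but can still contribute under the common-baseline-mean model, which favors that form if baseline samples are likely to be missing.
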